Appendix D. Quality Control and Quality Assurance

Important Protocol Deviations

Deviations from the study conduct due to emergency situations (eg, COVID-19 outbreaks), including implemented contingency measures and their impact (eg, patient discontinuation from treatment with investigational medicinal product and/or study, alternative procedures used to collect critical safety and/or efficacy data, etc), will be described in the appropriate sections of the CSR as applicable.

Study Monitoring

In case of an emergency situation (eg, COVID-19 outbreaks), monitors may not be able to access the investigational centers for on-site visits in a timely manner. A remote monitoring risk mitigation plan will be utilized for sites where on-site monitoring visits are not permitted due to an increased public health risk, in accordance with IRB/EC approval and current guidance ([GUIDANCE, 2021](#)). Details are provided in the monitoring plan.

Appendix K. Rules for Pulmonary Function Testing

PFTs – When should you continue to test your subjects?

The protocol and pulmonary function testing equipment indicates when it is okay to continue testing your subjects for the TEV-48574 trial. Here are some guidelines for you to follow with your subjects:

1. Pulmonary function testing MUST follow ATS (American Thoracic Society) Standards (Graham 2019)

This means:

- a) At least 3 good quality spirometry efforts must be done for every spirometry session.
- b) You can do up to 8 efforts to achieve this 3 good quality effort requirement
- c) The values from the top 2 spirometry efforts MUST BE WITHIN 150 mLs of each other. This applies to both FEV1 and FVC.
- d) When you are done with the Pre-BD spirometry, the Spirotrac will give you an alert **IF** the Pre-BD efforts did NOT meet the ATS standards. **STOP TESTING**. You should not perform post-BD spirometry

2. Protocol Criteria

- a) The best FEV1 obtained at the screening visit, and at the Day of Randomization visit, MUST BE WITHIN 30% and 80%. Values outside of this range means the subject should stop testing.
- b) If this out of range PFT testing occurs at screening, the PFT testing must stop, and the subject can return within 2 weeks to try again to meet the spirometry entrance criteria.
- c) If this excursion of PFTs occurs on the Day of Randomization, the subject is a Randomization Failure, but may come back once again to rescreen for the study.

3. Retesting for Reversibility

- a) **If** the subject has done acceptable and repeatable spirometry for the Pre-BD testing at visit S1, and the subject **cannot reverse** at least 12% after bronchodilator administration at this S1 visit, then the subject is allowed to return to the office within two weeks after initial Screening visit, to try again to meet the spirometry criteria.
- b) Again, spirometry must also meet the ATS standards and the Protocol standards identified above.

**LIST OF ABBREVIATIONS AND DEFINITIONS OF TERMS**

Abbreviation	Term
ACQ-6	Asthma Control Questionnaire 6-question version
ADA	antidrug antibodies
ALP	alkaline phosphatase
ALT	alanine aminotransferase
ANCOVA	analysis of covariance
AST	aspartate aminotransferase
BMI	body mass index
CAE	clinical asthma exacerbation
CRF	case report form
CI	Confidence interval
COVID-19	coronavirus disease 2019
CV	coefficient of variation
DoR	Day of randomization
e-diary	electronic diary
ECG	electrocardiogram/electrocardiography
EOS	end of study
EOT	end of treatment
ER	emergency room
ET	early termination
mITT	modified intent-to-treat
PEF	Morning peak expiratory flow
FeNO	Fractional exhaled nitric oxide
FEV 1	forced expiratory volume in the first second
FSH	follicle stimulating hormone
HBsAg	hepatitis B surface antigen
HCG	Human chorionic gonadotropin
HIV	human immunodeficiency virus
HCV	hepatitis C virus
ICE	intercurrent events
ICS	inhaled corticosteroid
IMP	investigational medicinal product

Abbreviation	Term
ITT	intent-to-treat
JSRC	joint safety review committee
KM	Kaplan-Meier
LABA	Long-acting beta agonist
LoAC	loss of asthma control
LS	least square
MedDRA	Medical Dictionary for Regulatory Activities
MMRM	mixed model for repeated measures
NRS	numerical response scale
PDAESI	protocol-defined adverse events of special interest
PP	per-protocol
Proof of concept	POC
R&D	Research and Development
RTSM	Trial Supply Management
SABA	short-acting beta agonist
SAP	statistical analysis plan
sc	subcutaneous(ly)
SD	standard deviation
SE	standard error
SI	standard international
SOC	system organ class
SOP	standard operating procedure
ULN	upper limit of normal
UN	unstructured covariance
WHO Drug	World Health Organization Drug Dictionary

## INTRODUCTION

This Statistical Analysis Plan describes the planned analysis and reporting for Teva Branded Pharmaceutical Products R&D, Inc. study TV48574-AS-20031, [A 16-Week, Randomized, Double-Blind, Placebo-Controlled, Parallel-Group, Proof-of-Concept Study to Evaluate the Efficacy and Safety of TEV-48574 in Adults with T2-low/non-T2 Severe Uncontrolled Asthma], and was written in accordance with [REDACTED] (Statistical Analysis Plan).

The reader of this SAP is encouraged to read the study protocol (Protocol with Amendment 02 Approval Date: 28 April 2021) for details on the conduct of this study, the operational aspects of clinical assessments, and the timing for completing the participation of a patient in this study.

The SAP is intended to be in agreement with the protocol, especially with regard to the primary and all secondary endpoints and their respective analyses. However, the SAP may contain more details regarding these particular points of interest, or other types of analyses (eg, other endpoints). When differences exist in descriptions or explanations provided in the study protocol and this SAP, the SAP prevails; the differences will be explained in the clinical study report.

## 1. STUDY ENDPOINTS

### 1.1. Primary Efficacy Endpoints

The primary efficacy endpoint is the proportion of patients who experience loss of asthma control (LoAC) during the treatment period.

LoAC is defined as any one of the following during the treatment period:

- Morning PEF decrease  $\geq 30\%$  from baseline on 2 consecutive days or morning handheld FEV1 decrease  $\geq 20\%$  from baseline on 2 consecutive days
- Increase in SABA/quick-relief medication  $\geq 6$  puffs over baseline use in 24 hours on 2 consecutive days
- Increase in ICS dose  $\geq 4x$  most recent dose
- Systemic corticosteroid use
- Asthma ER visit or hospitalization

### 1.2. Secondary Efficacy Endpoints

Key secondary efficacy endpoints:

- Time from randomization to LoAC during the treatment period
- Asthma Control Questionnaire 6-question version (ACQ-6) at end of treatment (EOT) and throughout the study
- Forced expiratory volume in the first second (FEV1) (% predicted, L) at EOT and throughout the study
- Use of SABA quick relief medication at EOT and throughout the study

Other secondary efficacy endpoints:

- Proportion of patients who have a CAE during the treatment period
- Time from randomization to first CAE during the treatment period
- Number of nighttime awakenings due to asthma during the treatment period
- Percent decrease in ICS dose during the treatment period
- Other lung function parameters as assessed by hand-held spirometry at end of treatment (EOT) and throughout the study
- Fractional exhaled nitric oxide (FeNO) throughout the study

### 1.3. Safety Endpoints

Safety and tolerability endpoints:

- Frequency of adverse events
- Change from baseline in clinical laboratory test results (serum chemistry, hematology, and urinalysis) throughout the study
- Change from baseline in vital signs throughout the study
- Change from baseline in 12-lead electrocardiogram (ECG) findings throughout the study

- Use of concomitant medication
- Local tolerability
- Number (%) of patients who did not complete the study due to adverse events

#### 1.4. Device-Related Events

All device-related adverse events, malfunctions etc. will be recorded and evaluated for their impact relative to the safety and efficacy of the investigational medicinal product.

#### 1.5. Pharmacokinetic Assessment

Pharmacokinetic endpoints are

- Trough serum TEV-48574 concentrations throughout the study (sparse sampling)
- Population pharmacokinetic analysis of pharmacokinetic data

#### 1.6. Immunogenicity Assessment Endpoints

Immunogenicity endpoints are

Assessment of treatment-emergent anti-drug antibody (ADA) responses: change from baseline and throughout the study

Impact of the presence of ADAs on pharmacokinetics and clinical safety (if possible).

Assessment of neutralizing ADA in ADA positive patients throughout the study

#### 1.7. Estimand for Primary Efficacy Endpoint

An estimand, in general, includes 5 inter-related attributes – treatment condition, population of interest, variable (endpoint) of interest, intercurrent events (ICE) along with the strategy for handling ICE, and population-level summary for the endpoint. The four attributes of the estimand are defined as follows:

**Treatment condition:** TEV-48574 [REDACTED] vs. placebo administered bi-weekly in patients on stable background inhaled corticosteroids (ICS) / long-acting beta2 agonist (LABA) in the first four weeks but with background asthma controllers withdrawn in a structured manner from week 4 to week 8.

**Population:** The patients with T2-low and non-T2 uncontrolled severe asthma met all inclusion criteria and met none of the exclusion criteria.

The intent-to-treat (ITT) analysis set as defined in Section 3.1 will be the primary analysis set for efficacy. In the data analyses, the treatment will be assigned based on the treatment to which patients were randomized, regardless of which treatment they actually received.

**Variable:** The proportion of patients who experience LoAC during the 16-week treatment period due to the initially randomized treatment as actually taken (Mallinckrodt, 2013).

**Intercurrent events:** Early treatment discontinuation will result in a lack of exposure to the initially randomized treatment and the patient being put on alternative medications. Observations after IMP discontinuations may not reflect the treatment effects of the initially randomized

treatment. In addition, an early discontinuation prior to week 16 without LoAC will result in a missing observation of the primary efficacy endpoint altogether.

As the strategy to handle the ICEs for the primary analysis, each patient's treatment period is defined as from the first dose to the last dose + 14 days. Patients who withdraw from the study prior to week 16 without LoAC or early terminated the study treatment without experiencing LoAC during the patient's treatment period will be analyzed as having experienced LoAC, if the assessed reason of discontinuation is lack of efficacy or due to an asthma-related adverse event. Patients who withdraw from the study without LoAC or early terminated treatments without experiencing LoAC during the patient's treatment period for other reasons will be analyzed as having not experienced LoAC.

**Population-level summary:** Numbers and proportions of patients who experience LoAC during the treatment period, adjusted proportions estimated from the logistic regression analysis in the treatment groups, as well as odds ratios between the two treatment groups estimated from the logistic regression analysis.

## 2. STUDY DESIGN

### 2.1. General Design

This is a multicenter, randomized, double-blind, placebo-controlled, parallel-group proof-of-concept study to evaluate the efficacy and safety of TEV-48574 administered sc every 2 weeks in adult patients aged 18 years and older with T2-low and non-T2 uncontrolled severe asthma. The primary efficacy endpoint is the proportion of patients who experience loss of asthma control (LoAC) during the treatment period.

The study will consist of a 5-week period consisting of screening followed by a run-in, a 16-week treatment period, and an 8-week follow-up period.

#### *Screening and run-in (5 weeks)*

Screening starts with the initial screening visit and will be followed by a run-in that proceeds through the day prior to the day of randomization. The duration of the screening and run-in period will be 5 weeks and may be extended by up to 14 days to allow for IMP shipping and to complete assessments of peripheral blood eosinophil count. Screening assessments and procedures will be completed over at least 2 visits, including the initial screening visit, and may be completed over more than 2 visits. An effort should be made to complete screening assessments and procedures in the first 2 weeks following the initial screening visit, with the exception of the samples for the second (and if applicable third) peripheral blood eosinophil counts.

#### *Treatment Period (16 weeks)*

The treatment period begins with randomization and ends with the EOT visit (week 16). After the end of the screening period, patients who meet all of the inclusion criteria, none of the exclusion criteria, and all of the randomization criteria will be randomized in a 1:1 ratio to the following regimens administered sc every 2 weeks:

- TEV-48574 [REDACTED]
- Placebo to match TEV-48574

With randomization, patients enter the 16-week treatment period. The patients will receive the IMP [REDACTED]

Patients should be observed for 2 hours after the end of the first (loading dose) and second (first maintenance dose) administration of IMP and for 1 hour after the subsequent IMP administrations.

#### *Follow-up Period (8 weeks)*

[figure not shown]
After the end of the 16-week treatment period, the patient will enter the 8-week follow-up period for continued assessments. During the follow-up period, patients may resume their study-provided background controller therapies. This follow-up visit marks the end of study (EOS). Patients who complete the EOS visit will be considered to have completed the study.

Statistical Analysis Plan

The study duration will be approximately 18 months. The study is expected to start in Q3 2020 and last until approximately Q1 2022. The expected duration of the study may also be extended dependent on enrollment, sample size adjustment, and other factors.

The screening and run-in, treatment, and follow-up periods are described below; the study schematic diagram is presented in [Figure 1](#).

**Figure 1: Overall Study Schematic Diagram**

ACQ-6 = 6-question Asthma Control Questionnaire; CBC = complete blood count; DoR = day of randomization; EOS = end of study; EOT = end of treatment; FeNO = fractional exhaled nitric oxide; F/U = follow up; IMP = investigational medicinal product.

**2.2. Randomization and Blinding**

This is a randomized, double-blind study. Patients who meet all inclusion criteria, none of the exclusion criteria, and all of the randomization criteria will be randomly assigned to receive TEV-48574 or placebo to match TEV-48574 in a 1:1 ratio to the following regimens administered sc every 2 weeks:

- TEV-48574 [REDACTED]
- Placebo to match TEV-48574

Patients will be randomly assigned to treatment groups by means of a computer-generated randomization list. The specifications for randomization will be under the responsibility and oversight of Teva Global Statistics.

The study patients and the clinical team at the site will be blinded to treatment assignment until the database is locked for analysis. Individuals who may not be blinded include (but are not

limited to) the bioanalytical scientists, pharmacokineticists, and biostatisticians who are not directly involved in study conduct.

The randomization list will be assigned to the relevant treatment groups through a qualified service provider, eg, via the Randomization and Trial Supply Management (RTSM) system. The generation of the randomization list and management of the RTSM system will be done by a qualified service provider under the oversight of the responsible function at Teva.

### **2.3. Joint Safety Review Committee**

A Joint Safety Review Committee (JSRC) will convene and review all available safety data at specific stages of the study and will recommend proceeding with the study as planned, performing modifications, suspending study until further notice, or prematurely terminating the study.

Details are in JSRC Charter.

### **2.4. Sample Size and Power Considerations**

The primary efficacy analysis for this study will be the comparison between treatment groups of the proportion of patients experiencing a LoAC event during the 16-week treatment period. The study will be considered positive if the primary efficacy test indicates a statistically significant treatment effect versus placebo at the predefined significance level.

Sample size calculations were performed based on the following considerations:

In the Phase 2a study results for dupilumab, the observed LoAC rate in the placebo group was 44% (Wenzel et al 2013). The patients in that study had elevated peripheral blood eosinophil counts ( $\geq 300$  cells/ $\mu\text{L}$ ). To estimate the LoAC rate that would have been observed in patients with peripheral blood eosinophil counts  $< 300$  cells/ $\mu\text{L}$ , the ratio of exacerbation rates observed between eosinophil count strata in the placebo groups of the dupilumab Phase 3 study were used (Castro et al 2018). This resulted in an estimated LoAC rate of 27% for the patients meeting the entrance criteria for the current study.

This study is designed to detect a 60% reduction in LoAC rate versus placebo; ie, a placebo group rate of 27% and a TEV-48574 group rate of 10.8%.

Based on the assumptions above, and assuming a 15% dropout rate during the study, 62 randomized patients per treatment group will provide 80% power to detect a treatment effect of 60% reduction in LoAC rate in the TEV-48574 group with one-sided alpha (Type I error rate) of 0.1 with a Fisher's exact test.

An unblinded interim analysis is planned to re-assess the sample size and conduct a futility analysis as described in Section 13. If the sample size increases as a result of the interim analysis, the number of evaluable patients would be expected to increase proportionately.

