3.2. Planned Number of Patients and Countries

Approximately 310 patients will be screened to achieve approximately 62 randomized patients per arm (124 in total). An unblinded interim analysis (described in Section 9.12) is planned, which could result in a sample size increase, from the initially planned 124 to up to 174 total randomized patients (87 per arm), which would require up to 435 patients screened.

Assuming a dropout rate of approximately 15%, the number of evaluable patients is planned to be approximately 52 per arm (104 in total). If the sample size increases as a result of the interim analysis, the number of evaluable patients would be expected to increase proportionately (eg, approximately 148 evaluable patients for a sample size of 174 patients randomized). Details on definition of evaluable patients and sample size are given in Section 8.4.

The study is planned to be conducted in the United States and the European Union across approximately 75 investigational centers in approximately 5 countries. Additional geographic locations and investigational centers may be added, if needed.

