9.1. Sample Size and Power Considerations

The primary efficacy analysis for this study will be the comparison between treatment groups of the proportion of patients experiencing a LoAC event during the 16-week treatment period. The study will be considered positive if the primary efficacy test indicates a statistically significant treatment effect versus placebo at the predefined significance level.

Sample size calculations were performed based on the following considerations:

In the Phase 2a study results for dupilumab, the observed LoAC rate in the placebo group was 44% (Wenzel et al 2013). The patients in that study had elevated peripheral blood eosinophil counts (≥ 300 cells/ μL). To estimate the LoAC rate that would have been observed in patients with peripheral blood eosinophil counts < 300 cells/ μL , the ratio of exacerbation rates observed between eosinophil count strata in the placebo groups of the dupilumab Phase 3 study were used (Castro et al 2018). This resulted in an estimated LoAC rate of 27% for the patients meeting the entrance criteria for the current study.

This study is designed to detect a 60% reduction in LoAC rate versus placebo; ie, a placebo group rate of 27% and a TEV-48574 group rate of 10.8%.

Based on the assumptions above, and assuming a 15% dropout rate during the study, 62 randomized patients per treatment group will provide 80% power to detect a treatment effect of 60% reduction in LoAC rate in the TEV-48574 group using a Chi-square test with one-sided alpha (Type I error rate) of 0.1.

An unblinded interim analysis is planned to re-assess the sample size and conduct a futility analysis as described in Section 9.13. If the sample size increases as a result of the interim analysis, the number of evaluable patients would be expected to increase proportionately.

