### 6.2.2. Primary Efficacy Analysis

The primary analysis will compare rates of LoAC between treatment groups using logistic regression with fixed effect for treatment, age group (<65 years vs  $\geq 65$  years) and gender, as well as baseline FEV1 and baseline weight as covariates. Patients who withdraw from the study before the week 16 or early terminated the study treatment due to lack of efficacy, LoAC, or an asthma-related adverse event will be analyzed as having experienced LoAC. Patients who withdraw from the study before the week 16 without LoAC or early terminated from the study treatment without experiencing LoAC during the patient's treatment period (Section 1.7) for other reasons will be analyzed as not experiencing LoAC. Asthma-related adverse events will be determined by blinded data reviews prior to the final database lock.

The treatment effect will be tested at a one-sided alpha of 0.1.

The primary analysis will be performed on the ITT analysis set. The rates of LoAC for each treatment group, confidence intervals, and p-value will be displayed.

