**Table 5: Calculated Type 1 Error Rates with or without Sample Size Re-assessment**

True Placebo Event Rate	Fixed Sample Size Design	Adaptive Sample Size Design
0.12	10.5%	9.5%
0.15	10.3%	9.7%
0.18	10.3%	10.0%
0.21	10.4%	10.2%
0.24	10.2%	10.1%
0.27	10.1%	10.0%
0.30	10.3%	10.3%
0.33	10.6%	10.6%
0.36	10.7%	10.7%
0.39	10.3%	10.3%
0.42	9.7%	9.7%
0.45	9.2%	9.2%

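### SAP 2.4 credits its 80% power to Fisher's exact test, which gives about 74% under the stated assumptions; the 80% belongs to the chi-square test in Protocol 9.1

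*SAP*

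**What the plan says.** SAP section 2.4 sets the design alternative as "ie, a placebo group rate of 27% and a TEV-48574 group rate of 10.8"%, assumes 15% dropout, and says that "62 randomized patients per treatment group will provide 80% power". It sets the one-sided alpha and the test in the words "Type I error rate) of 0.1 with a Fisher", followed by the rest of the test's name.

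Protocol section 9.1 and the protocol synopsis carry the same rates, dropout, sample size, power and alpha, but with a different test: "TEV-48574 group using a Chi-square test with one-sided alpha (Type I error rate) of 0.1".

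Protocol section 3.2 turns the dropout assumption into an analysed number: "the number of evaluable patients is planned to be approximately 52 per arm (104 in total").

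The planned primary test is neither of these. SAP section 6.2.2 says: "The primary analysis will compare rates of LoAC between treatment groups using logistic regression with fixed effect for treatment", adjusted for baseline FEV1, weight, age group and gender.

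On precedence, the SAP Introduction says: "When differences exist in descriptions or explanations provided in the study protocol and this SAP, the SAP prevails". SAP section 15 lists no changes from the protocol.

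**The concern.** Fisher's exact test and the uncorrected chi-square test do not have the same power at about 50 patients per arm. Fisher's test is conservative: its actual one-sided size is well under the nominal 10%, and it loses power accordingly. The same 80% from the same inputs therefore cannot be right for both tests.

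The SAP version governs, and it is the one in doubt. A reader who checks SAP 2.4 as written would find a shortfall and might wrongly conclude that the trial was sized too small. The stake is the traceability of the sample-size justification, not the inference.

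**Working it through.** **Inputs.** Placebo rate 0.27, TEV-48574 rate 0.108, one-sided alpha 0.10, 1:1 allocation, 62 randomized per arm, 15% dropout (SAP 2.4; Protocol 9.1). Evaluable per arm: 62 × 0.85 = 52.7, planned as about 52 (Protocol 3.2). The interim look is ignored, because the documents describe this power calculation without it.

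**Step 1. Reproduce the plan's figure with the chi-square test.** Difference 0.27 − 0.108 = 0.162; pooled rate (0.27 + 0.108)/2 = 0.189.

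- Required n per arm = [1.2816·√(2 × 0.189 × 0.811) + 0.8416·√(0.27 × 0.73 + 0.108 × 0.892)]² / 0.162² = 51.8, so 52. Then 52/0.85 = 61.2, so 62 randomized.
- Null standard error at 52 per arm: √(2 × 0.189 × 0.811/52) = 0.0768. Under the alternative: √((0.27 × 0.73 + 0.108 × 0.892)/52) = 0.0751.
- Power = Φ[(0.162 − 1.2816 × 0.0768)/0.0751] = 80.1%.
- Exact enumeration of the uncorrected chi-square test at 52 per arm gives 80.7%.

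Both the 62 and the 80% come out.

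**Step 2. The same inputs with Fisher's test.** For each pair of event counts (i on placebo, j on TEV-48574) with n per arm, the one-sided p-value is the hypergeometric probability of i or more placebo events given i + j in total. Power is the sum of the binomial probabilities of all pairs with p ≤ 0.10.

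| Analysed per arm | Fisher | Chi-square (exact) |
|---|---|---|
| 52 | 73.6% | 80.7% |
| 53 | 74.4% | 81.4% |
| 62, no dropout | 79.8% | 86.3% |
| 62, 15% dropouts as non-events | 72.0% | 80.7% |

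The last row uses diluted rates: 0.27 × 0.85 = 0.2295 and 0.108 × 0.85 = 0.0918. Fisher first reaches 80% at 63 evaluable per arm (80.5%). That is 63/0.85 = 74.1, so 75 randomized per arm.

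**Step 3. The planned type of test.** Unadjusted logistic regression at 52 per arm, by the same enumeration, gives 80.7% (likelihood ratio) or 80.5% (Wald). With all 62 kept and dropouts as non-events it gives 80.7% and 80.3%. Power of the adjusted model needs covariate effects that the documents do not give.

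**Step 4. A check inside the SAP.** The fixed-design column of SAP Table 5 ("Calculated Type 1 Error Rates with or without Sample Size Re-assessment") runs from 9.2% to 10.7%, with ten of its twelve entries above 10%. Fisher's test cannot exceed its nominal level; at 62 per arm it gives 5.7% to 7.7% over the same placebo rates. The chi-square test at 62 per arm gives 10.5, 10.3, 10.3, 10.4, 10.2, 10.1, 10.3, 10.6, 10.7, 10.3, 9.7 and 9.2%, the whole column. The unadjusted likelihood-ratio test gives the same values, so Table 5 rules out Fisher but does not single out chi-square.

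**The case against.** The best defence is that Fisher's test with 62 analysed patients per arm has 79.8% power, which rounds to 80%. The intent-to-treat set keeps every randomized patient and assigns dropouts an outcome, and Table 5 fits 62 per arm rather than 52. If 27% and 10.8% are read as rates in all randomized patients, the SAP sentence is nearly reproducible.

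That reading does not survive the sentence itself, which assumes 15% dropout, or Protocol 3.2, which plans about 52 evaluable per arm. Nor does keeping all 62 help once dropout is allowed for: patients who leave for reasons unrelated to asthma count as not having LoAC, and if all 15% do so Fisher's power is 72.0%. What stands is that the 74% depends on the analysed number, and that the chi-square origin of the 80%, though well supported, is an inference.

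It is also fair to say that little hangs on the word. The primary and futility tests are logistic regressions, the sample-size increase depends on observed event rates, and the protocol labels the calculation correctly. Table 5 is only supporting evidence: it names neither its test nor its sample size and concerns the re-assessment, not the power statement. These points limit the consequence. They do not make the stated power correct for the named test.

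**Conclusion.** The concern holds. As written, SAP 2.4 overstates the power of its named test by about 6 points: 73.6% at 52 or 74.4% at 53 evaluable per arm, against 80%. This rests on the documents' own rates, one-sided alpha and dropout, with dropouts either excluded or, at 72.0%, counted as non-events.

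The mismatch is a wrong statement in a governing document, and it should be corrected. It is not evidence that the trial is too small, and it touches neither the type I error nor the primary analysis.

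**What to change.** In SAP 2.4, replace Fisher's exact test with the chi-square test, matching Protocol 9.1; the 62 per arm and 80% then stand as printed. If Fisher's test was intended, restate the power as about 74%, specifying 52 to 53 evaluable per arm, and record the change of test in SAP section 15.

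The cost is one line of wording for the first option, plus the section 15 entry for the second. Neither changes enrolment, alpha or the primary analysis.
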